After low molecular weight heparin is administered, it predominantly concentrates in the plasma and highly vascular tissues with little distribution into fat tissue. Since dosing is based on weight, obese patients may receive higher doses; however, because there is low distribution into fat tissue this may result in elevated anti-Xa levels and thus they can be easily overdosed. It has been shown that anti-Xa activity is increased appropriately when the drug is administered to patients based on total body weight up to 144 kg. The American College of Chest Physicians Evidence-based clinical practice guidelines recommend monitoring of anti-Xa levels in obese patients. Enoxaparin has both anti-Xa and anti-IIa activity however, because of the higher anti-Xa:IIa ratio, anti-Xa levels are used as a marker of activity. It has been suggested that the incidence of bleeding is increased when anti-Xa levels are elevated; however, data are conflicting.

There is limited data available to guide dosing of patients above 150 kg. The largest prefilled syringe is 150 mg and has resulted in many clinicians capping the dose at 150 mg. A pharmacokinetic study in 48 healthy obese volunteers (BMI 30-40  $\text{kg/m}^2$ ) at a single study center showed that dosing based on total body weight achieved similar maximum anti-Xa levels in both obese and non-obese patients, 1.563 IU/ml and 1.488 IU/ml respectively. The authors recommended no need to modify dosing in obese patients; however, this trial used 1.5 mg/kg daily, included healthy volunteers, and the highest weight studied was only 144 kg. A prospective study in hospitalized patients with a BMI $>30 \text{ kg/m}^2$  evaluated anti-Xa levels using 1 mg/kg twice daily. Forty five percent of patients achieved a therapeutic anti-Xa level with the mean being 1.17 IU/ml. There was no difference in anti-Xa levels between those with and without bleeding episodes. The authors concluded no dose adjustment necessary in this study. The results from the above studies suggest standard dosing produces similar anti-Xa levels in non-obese and obese patients above 30  $\text{kg/m}^2$ .

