#### iii. Initial anti-Xa levels

1. Order levels 4 hours after at least three consecutive study doses of enoxaparin (will allow levels drawn between 3-5 hrs). If the level is not drawn, it will be reordered after the next dose.
2. Therapeutic anti-Xa: 0.5-1.1 IU/ml (GHS therapeutic range)
3. Adjustments will be made according to the dosing nomogram until a therapeutic level is obtained (see appendix). If a bleeding event occurs an anti-Xa level will be obtained.

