##### 2. Post intervention

- a. Scr, CrCl

- b. Initial dose of enoxaparin (mg/kg and mg)
  - c. Initial anti-Xa level and timing of level
  - d. Number of hours post dose
    - i. Level at 4 hours
    - ii. Level within range of 3-5 hours
  - e. Total number of doses received prior to level
- 3. Subsequent doses of enoxaparin (mg/kg and mg)
- 4. Subsequent anti-Xa levels after dosing adjustments
- 5. Time to first therapeutic anti-Xa level
- 6. Total days on enoxaparin
- 7. Bleeding events
  - a. Decrease in Hgb
  - b. Site of bleed
  - c. Blood product use
  - d. INR at onset of bleeding event for patients on warfarin
  - e. Additional anticoagulants and antiplatelets (date initiated and dose)
  - f. Platelet count at onset of bleeding event
  - g. Anti-Xa level at onset of bleeding event
  - h. PT and/or aPTT if available
- v. Respondent Burden-Total respondent burden will be minimal and depend on the time it takes to consent. Laboratory work would have to be done for this medication regardless of whether they were in the study or not.

e. Study Objectives/Outcomes

- i. Primary Objective
  - 1. To determine if enoxaparin dosing using 0.8mg/kg is more effective for achieving therapeutic steady state anti-Xa levels in morbidly obese patients when compared to 1 mg/kg dosing. (Morbid obesity is defined as a BMI > 40 kg/m^2)
- ii. Secondary Objectives
  - 1. To compare time to therapeutic anti-Xa levels for both dosing regimens
  - 2. To compare anti-Xa levels for both dosing regimens
  - 3. To compare number of dose adjustments required to achieve therapeutic anti-Xa levels using a dosing nomogram
  - 4. To validate dosing nomogram used to adjust low molecular weight heparin doses
  - 5. To evaluate major and minor bleeding events
- iii. Primary Outcome
  - 1. Proportion of patients with an initial therapeutic anti-Xa level at steady state in each group
    - a. Peak anti-Xa drawn 3-5 hours post dose after receiving at least 3 consecutive doses
- iv. Secondary Outcomes
  - 1. Time to therapeutic anti-Xa level for both groups
  - 2. Mean/Median therapeutic anti-Xa level for both groups
  - 3. Mean/Median number of dose adjustments required to achieve therapeutic anti-Xa level for both groups
  - 4. Proportion of patients with major and minor bleeding events (will follow until anti-Xa level is therapeutic)

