- a. Major bleed: Hgb drop of  $\geq 2\text{g/dL}$ , transfusion of 2 or more units of blood products, or retroperitoneal, intraocular, or intracranial hemorrhage
- b. Minor bleed: bleeding events not meeting major bleed criteria
- f. Risks to participation
  - i. Patients started on enoxaparin will be at risk for bleeding complications which is a known risk for this medication. Risk will be reduced by obtaining anti-Xa levels and adjusting the dose as needed. Other possible risks may be , anemia, decrease in platelets, elevation of liver enzymes, diarrhea, and nausea
- g. Benefits to subject or future benefits
  - i. By completing this study a strategy for dosing enoxaparin may be established for obese patients that is safer and allows for quicker therapeutic levels.
- h. Data analysis
  - i. Sample Size- In order to detect a 15% difference in the primary endpoint with a 2-sided significance level of 0.05, 50 patients per dosing group is needed to provide 80% power.
  - ii. Statistical Analysis
    - 1. Descriptive statistics will be used for all variables. Primary outcome will be analyzed using chi-square. Time to event will be analyzed using survival curves and log rank test. Medians will be compared using wilcoxon rank test.

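### The bleeding outcome stops at the first therapeutic anti-Xa level, so later bleeds on the continued dose are not counted

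*Combined protocol and SAP*

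**What the plan says.** The bleeding objective (section 2.e.ii, item 5) has no time limit: "To evaluate major and minor bleeding events". The matching outcome (section 2.e.iv, item 4) has one: "Proportion of patients with major and minor bleeding events (will follow until anti-Xa level is therapeutic").

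The event that closes this window is set in section 2.d.iii. Item 1 is "Order levels 4 hours after at least three consecutive study doses of enoxaparin", with draws accepted at 3 to 5 h. Item 3 ends titration at the same event: "Adjustments will be made according to the dosing nomogram until a therapeutic level is obtained". In Appendix A, the row for 0.5-1.1 IU/mL shows no held dose, no dose change and no repeat level.

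Other text on bleeding has no end date. Section 2.d.iv lists details of bleeding events and "Total days on enoxaparin". Section 2.d.iii and the Appendix A footnote call for a level if a bleed occurs. Section 4 says that safety data, specifically bleeding, will be collected as already described.

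For analysis, section 2.h.ii says "Descriptive statistics will be used for all variables" and names no test for bleeding. Section 2.g gives as a possible benefit that "a strategy for dosing enoxaparin may be established for obese patients that is safer".

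**The concern.** A patient whose first level is in range stays on the assigned dose, and that is when bleeding follow-up for the outcome ends. For these patients the starting dose did what it was meant to do, yet their later bleeds on it are left out. The reported proportion describes the titration phase and says little about bleeding on the dose that is kept. Bleeding is the only safety outcome listed, so any statement that one strategy is safer would rest on this short window.

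The window also closes on a post-randomisation result that the dose is meant to change. Time to that result is itself compared between arms (section 2.e.iv, item 1). The arm that reaches range sooner is watched for less time, so a raw proportion mixes bleeding risk with length of observation.

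**Working it through.** The plan gives no bleeding rate, course length or power for this outcome, so there is no figure of its own to reproduce.

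**1. Does any section extend the window?** The objective and the data list carry no limit, but neither redefines the outcome. Section 4 points back to data already described. The rules for a level at a bleed order a test and set no follow-up period. The limit in section 2.e.iv therefore stands.

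**2. Earliest end of follow-up.** Twice-daily dosing is from section 2.a.i; the 12 h interval is an assumption.
- Three study doses at 0, 12 and 24 h, then a draw 3, 4 or 5 h later: 24 + 3 = 27 h, 24 + 4 = 28 h, 24 + 5 = 29 h.
- Share of an assumed course covered by 28 h: 28/72 = 39% (3 days); 28/120 = 23% (5 days).
- With one adjustment, 28 + 12 = 40 h: 40/72 = 56%; 40/120 = 33%.

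Reordered levels and held doses would lengthen the window and are not modelled.

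**3. Effect of unequal follow-up between arms.** Assumptions:
- In range at first level: 60% vs 45%. The 45% is the Background figure for hospitalised patients with BMI >30 on 1 mg/kg twice daily; the gap is the 15 points in section 2.h.i.
- Success at each 12-hourly repeat level: q = 30% to 80%.
- Bleeding risk after range: r = 1% to 2% per day; before range: k times r; same in both arms.

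Mean window = 28 + 12(1 − p)/q, where p is the proportion in range at the first level:

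| q | p = 0.60 | p = 0.45 |
|---|---|---|
| 0.3 | 44.0 h | 50.0 h |
| 0.5 | 37.6 h | 41.2 h |
| 0.8 | 34.0 h | 36.25 h |

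The arms differ only in the 15% of patients who need at least one repeat in one arm and none in the other. With hourly hazard h = k·r/24 and course length L, the excess of counted patients per 50 in the slower arm is

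50 × 0.15 × {exp(−28h) − Σ q(1−q)^(n−1) exp(−h·min(28+12n, L))}, summed over n ≥ 1.

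- Constant risk (k = 1), no limit on course length: 0.05 to 0.24. The largest value (q = 0.3, r = 2%) is 7.5 × (0.9769 − 0.9452) = 0.24.
- Constant risk, 2-day course: 0.04 to 0.11.
- Constant risk, 5-day course: 0.05 to 0.22. The largest value is 7.5 × (0.9769 − 0.9472) = 0.22.
- Fourfold risk before range (k = 4), 5-day course: 0.18 to 0.78. The largest value is 7.5 × (0.9109 − 0.8071) = 0.78.
- The excess is proportional to the gap. The Background also reports 46% at goal at a median 0.8 mg/kg with BMI ≥40. Set against the 45%, that is a 1-point gap, and 0.24 × 1/15 = 0.02.

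**The case against.** The strongest reply is that this is a choice of scope. The study's purpose is to reach therapeutic anti-Xa levels, the primary outcome is the initial level, and bleeding is a descriptive secondary outcome. Titration ends at the therapeutic level, so the window matches the intervention studied. After nomogram adjustment the two arms' doses may converge, so a longer window dilutes the contrast between starting doses. The Background's own rationale, "It has been suggested that the incidence of bleeding is increased when anti-Xa levels are elevated" (with the caveat there that data conflict), also points to the phase before range. All of this stands. It is a reason to keep the titration window, but not to make it the only one.

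The second reply is that bleeds after the therapeutic level would still be noticed. A reader might infer from the outcome that bleeding surveillance stops there, and the documents do not support that. Bleeding data, days on enoxaparin and the level at a bleed have no end date. Because the 0.5-1.1 row has no routine repeat, the natural reading of the Appendix A footnote is that a later bleed still prompts a level. Those bleeds may well be on file, but the plan does not say so and does not bring them into the outcome.

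**Conclusion.** The point holds as a limit on what the bleeding outcome counts. Followed as written, it omits on-treatment bleeds after the first therapeutic level. For a patient in range at once it covers about 27 to 29 h: roughly 39% of a 3-day course or 23% of a 5-day course. Course lengths and the 12 h interval are assumptions.

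A reader might go further and infer either that the bleeding comparison is materially biased between arms or that this bias is small whatever the circumstances. The documents support neither. At constant risk with a 15-point gap the effect is under about 0.25 patients per 50; with no gap it is near zero; with fourfold early risk it can reach about 0.8 per 50 over 5 days. The documents give neither the bleeding risk over time nor the success rate of repeat levels, so the size depends on assumptions.

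The weight is limited: no test is planned for this outcome and the primary analysis is untouched. It is worth considering because the remedy is cheap.

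**What to change.** Define the bleeding outcome over one window that does not depend on the anti-Xa result: from the first study dose to 12 h after the last inpatient enoxaparin dose, or to discharge, whichever is first. The 12 h is one assumed dosing interval and keeps a bleed that itself led to stopping.

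- Report by arm the proportion of patients with a bleed and the rate per inpatient day on enoxaparin, counting days over the same window, because its length still varies between patients. Leave out doses given before study entry.
- Show major bleeds separately.
- For patients excluded under section 4 for declining renal function, count bleeds and days up to exclusion, and note that this censoring may be informative.
- Keep the present window as a titration-phase analysis beside it.

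The cost is a few sentences in sections 2.e.iv and 2.h.ii and a longer chart review of items already listed. There are downsides. The starting-dose contrast is diluted after titration. Minor bleeds and haemoglobin may be recorded less completely once titration ends, since no haemoglobin schedule is given. Bleeds after discharge remain uncounted.

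### Major bleeding is a closed list of five criteria, so a fatal bleed or one at another critical site is scored as minor unless it also meets one of the five

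*Combined protocol and SAP*

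**What the plan says.** Section 2.e.iv, item 4 makes the proportion of patients with major and minor bleeding a secondary outcome, with follow-up until the anti-Xa level is therapeutic. Item 4a, citing reference 13 (the package insert), calls a bleed major if hemoglobin falls by at least 2 g/dL, or if there is "transfusion of 2 or more units of blood products, or retroperitoneal, intraocular, or intracranial hemorrhage". Item 4b completes the scheme: "Minor bleed: bleeding events not meeting major bleed criteria".

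Section 2.d.iv, item 7 lists what is recorded for each bleed: hemoglobin decrease, site, "Blood product use", INR for patients on warfarin, other antithrombotics, platelet count, anti-Xa level, and PT or aPTT if available. It has no field for death from the bleed and none for an intervention to stop it.

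Section 4 (data management and monitoring) refers back to these data and adds no further bleeding category. No section provides a third category, a rule for fatal bleeds, or adjudication that could override the label.

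**The concern.** The minor category is purely residual and has no upper bound on severity. Whatever fails all five major criteria falls into it, including a bleed that kills the patient before a second hemoglobin value or a second unit, or an intraspinal or pericardial bleed with little blood loss. This is not a missing detail: the stated rule, followed exactly, gives a wrong grade.

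Bleeding is the only safety outcome the protocol defines, and major versus minor is its only grading. The Background gives avoidance of bleeding complications as part of the need for the trial, and section 2.g holds out a safer dosing strategy as a benefit. A report could therefore state that a group had no major bleeds when one of its patients had died of a bleed.

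**Working it through.** The plan states no figure on this point to reproduce, so the check is to apply the rule to cases.

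**Rule, from section 2.e.iv, items 4a and 4b.** Major if (hemoglobin fall ≥ 2 g/dL) or (blood products ≥ 2 units) or (site is one of "retroperitoneal, intraocular, or intracranial hemorrhage"); otherwise minor.

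**Cases.** These are hypothetical and chosen to test the rule; none is a prediction.

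| Bleed | Hemoglobin fall (g/dL) | Units | Listed site? | Label |
|---|---|---|---|---|
| Fatal, pericardial | 1 | 0 | no | minor |
| Intraspinal | 0.5 | 0 | no | minor |
| Gastrointestinal, needing a procedure | 1.5 | 1 | no | minor |
| Nosebleed | 0 | 0 | no | minor |
| Fatal, gastrointestinal | 3 | 0 | no | major |
| Fatal, intracranial | 0 | 0 | yes | major |
| Gastrointestinal, needing a procedure | 1.5 | 2 | no | major |

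Death, an unlisted critical site, or a procedure never makes a bleed major by itself. The first three rows get the same label as a nosebleed. The last three show that such bleeds are still major when a listed criterion is also met.

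**Could the grade be corrected later from the data collected?** Using the fields in section 2.d.iv, item 7:

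- Other critical site: yes, because site is recorded.
- Fatal bleed: not reliably, because no field records it.
- Bleed needing intervention: not reliably, for the same reason.

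**Weight of one event.** The denominator comes from section 2.h.i ("50 patients per dosing group is needed to provide 80% power"), a size chosen for the primary endpoint, not for bleeding.

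- One event: 1/50 = 2.0 percentage points.
- Exact (Clopper-Pearson) two-sided 95% upper limit for 0/50: 1 − 0.025^(1/50) = 7.1%.
- Upper limit for 1/50: the p that solves (1 − p)^50 + 50p(1 − p)^49 = 0.025, which is 10.6%.

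These limits show what any single misplaced event does in a group of 50. They do not say how often this rule would misplace one.

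**The case against.** The strongest case on the other side has five parts.

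1. *Few severe bleeds escape all five criteria.* A reader might infer that fatal bleeds are routinely scored as minor. The text does not support that. The hemoglobin criterion carries no time limit and no requirement for overt bleeding, so it catches a lot, and many fatal bleeds would be major through hemoglobin, transfusion or site. This stands, and it is why the point is conditional.

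2. *Bleeding is not the trial's purpose.* The purpose sentence closing the Background concerns therapeutic anti-Xa levels. Prevention of bleeding appears in the rationale just before it, and bleeding is the last-listed secondary outcome. This also stands, and it limits the importance of the point without removing it.

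3. *The label drives little.* Under section 2.d.iii any bleed, whatever its grade, prompts an anti-Xa level. No stopping rule or named test uses the major category. Bleeds are counted only until the level is therapeutic, which may be a short window for many patients. All true; the consequence lies in what is reported.

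4. *The information is already there.* Site is collected and section 2.h.ii promises descriptive statistics for all variables, so a pericardial bleed would be visible whatever its label. That holds for site. It does not hold for fatal outcome or intervention.

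5. *The definition is cited, and keeping it is a legitimate choice.* Reference 13 is not among the documents, so a reader should not infer either that the protocol departs from its source or that it matches it. Comparability is a fair reason to retain the definition in a second tabulation. It does not make the grade right for a fatal bleed.

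A reader might also infer that any bleed needing a procedure should be major. That goes too far: with no definition of procedure, trivial local measures could count and create the opposite misclassification.

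**Conclusion.** The concern holds in conditional form: under items 4a and 4b, a fatal bleed or a bleed at an unlisted critical site is minor unless it also meets one of the five listed criteria.

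The number of events affected cannot be estimated, because the documents give no expected rate of bleeds that are severe yet meet none of the five. It is probably small. If one such event occurred, it would shift that group's major-bleed rate by 2 percentage points, assuming 50 evaluable patients per group. The 7.1% and 10.6% limits should not be read as the size of the flaw.

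This is worth correcting because it is a wrong grading rule in the only defined safety outcome, it costs almost nothing to put right, and part of it cannot be reliably repaired from the data now listed.

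**What to change.** 1. Extend item 4a in section 2.e.iv with: *or any bleed that is fatal or occurs at another critical site (e.g. intraspinal, pericardial, or intramuscular with compartment syndrome)*. The sites are examples offered for the sponsor's clinical agreement; they are not taken from the documents. Leave item 4b as the residual category.
2. Add two fields to section 2.d.iv, item 7: fatal outcome (yes/no) and intervention to stop the bleed (none, or type).
3. List bleeds needing surgical or endoscopic intervention individually in the report, without making any procedure a major criterion.
4. Report a second tabulation using the five criteria as they now stand, with reference 13.

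The cost is one line of definition and two items from the chart, with no extra visits, tests or patients. The downside is slightly less direct comparability with the cited definition, which the second tabulation offsets. The change should be made before data collection, since the two new fields may not be reliably recoverable afterwards.

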A retrospective study evaluating the dosing of enoxaparin in 26 morbidly obese hospitalized patients (BMI  $\geq 40 \text{ kg/m}^2$ ) also evaluated anti-Xa levels. A median dose of 0.8 mg/kg based on total body weight was utilized with maximum doses up to 150 mg. Forty six percent of patients achieved a goal anti-Xa level and 38% of patients were above the anti-Xa goal. The weight cut-off of 150 kg did not result in statistically significant differences in mean anti-Xa levels (1.12 IU/ml in patients over 150 kg vs 0.81 IU/ml in patients over 150 kg,  $p>0.05$ ). Even though 4 out

of 10 patients with a supratherapeutic anti-Xa level experienced more bleeding events, these patients were noted to have additional risk factors for bleeding. This trial suggests that lower initial dosing of enoxaparin could be utilized in the morbidly obese population since the majority of anti-Xa levels were at or above goal.

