### d. Procedures

- i. Eligible patients will be approached while inpatient for written consent
- ii. Patients will be randomized in a 1:1 fashion into the 0.8mg/kg or 1 mg/kg group (using total body weight) stratified by BMI
  1. Doses will be rounded to the nearest 10mg due to graduations on syringe

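### Fifty patients per group do not give 80% power for a 15-point difference; at the response rates the protocol cites, power is about 32–35%

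*Combined protocol and SAP*

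**What the plan says.** Section 2.h.i is the only sample size justification in the document: "15% difference in the primary endpoint with a 2-sided significance level of 0.05, 50 patients per dosing group is needed to provide 80% power". It does not give the expected rate in either group, say whether 15% is absolute or relative, or allow for dropout.

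The other inputs are stated elsewhere:

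- Allocation (Section 2.d.ii): "Patients will be randomized in a 1:1 fashion into the 0.8mg/kg or 1 mg/kg group".
- Primary outcome (Section 2.e.iii), which is binary: "Proportion of patients with an initial therapeutic anti-Xa level at steady state in each group".
- Therapeutic range (Section 2.d.iii): 0.5 to 1.1 IU/ml, so a level above 1.1 is not a success.
- Primary test (Section 2.h.ii): chi-square.

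The Background gives two on-target rates. For 1 mg/kg twice daily in hospitalized patients with BMI above 30: "Forty five percent of patients achieved a therapeutic anti-Xa level with the mean being 1.17 IU/ml". For a median of 0.8 mg/kg in 26 hospitalized patients with BMI of at least 40: "Forty six percent of patients achieved a goal anti-Xa level and 38% of patients were above the anti-Xa goal".

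**The concern.** The sample size needed to compare two proportions depends heavily on where the proportions lie. A 15-point difference is most expensive to detect near 50%, and the cited rates are close to 50%. Fifty per group is far too few there, so the omitted response rate is more than a reporting gap: no rate that the protocol mentions for this endpoint makes the stated figures agree.

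The statement concerns the primary endpoint, and the Background says that the eventual aim is a dosing and monitoring protocol. If the trial carries an 80% power label but has about one chance in three of detecting the difference it names, a non-significant result could be misread as showing that the two doses perform alike.

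**Working it through.** **Inputs.** Two-sided α = 0.05 (z = 1.960), power 80% (z = 0.842), n = 50 per group and a difference of 0.15, read as absolute, all from Section 2.h.i; 1:1 allocation from Section 2.d.ii; on-target rates of 45% and 46% from the Background.

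**Formulas** (pooled normal approximation, with p̄ the mean of p₁ and p₂, and Φ the standard normal distribution function):

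- n per group = {1.960·√[2p̄(1−p̄)] + 0.842·√[p₁(1−p₁)+p₂(1−p₂)]}² / (p₁−p₂)²
- power = Φ{ (|p₁−p₂|·√n − 1.960·√[2p̄(1−p̄)]) / √[p₁(1−p₁)+p₂(1−p₂)] }

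**Step 1: reproduce the plan's figure.** A scan of every whole-percent baseline from 0% to 85% with a 15-point increase comes close to 50 only at the two ends.

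- 0% vs 15%, or 85% vs 100%: n = (0.730 + 0.301)² / 0.0225 = 47.2, so 48 per group; power at 50 is 82.3%.
- One point further in (1% vs 16%, or 84% vs 99%): n = 53.1, so 54 per group; power at 50 is 77.6%.

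**Step 2: use the cited rate.** For 45% vs 60%, p̄ = 0.525.

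- n = (1.384 + 0.588)² / 0.0225 = 172.8, so 173 per group, and 173/50 ≈ 3.5 times the stated number.
- Power at 50: (0.15 × 7.071 − 1.384) / 0.698 = −0.463, and Φ(−0.463) = 32.2%.
- Exact enumeration of the uncorrected chi-square test: 34.5%. With Yates correction: 27.3%.

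Starting from 46% (46% vs 61%) gives n = 172.4, so 173 per group, and power of 32.2%.

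**Step 3: vary the baseline.** For a 15-point increase with 50 per group:

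| Rates | Power at 50 per group | n per group for 80% |
|---|---|---|
| 20% vs 35% | 39% | 138 |
| 30% vs 45% | 34% | 163 |
| 45% vs 60% | 32% | 173 |
| 60% vs 75% | 36% | 152 |
| 75% vs 90% | 51% | 100 |
| 80% vs 95% | 62% | 76 |

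For lower rates from 20% to 60%, power stays between 32% and 39%. A 15-point decrease from 45% (45% vs 30%) gives 34%.

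**Step 4: try other readings at the cited rates.** None reaches 80%.

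- One-sided 0.05: 44–46%.
- 100 per group: 57–59%.
- 50 patients in total: 18–19%.
- A relative 15% (45% to 0.45 × 1.15 = 52%): about 10%.

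**Step 5: what 50 per group can detect.** From 45%, 80% power is reached at an increase of 27.3 points. At 45% vs 72%, power is 79% by the pooled formula and 80% by exact enumeration. At 45% vs 60%, the 95% CI half-width is 1.96 × √[(0.45×0.55 + 0.60×0.40)/50] = 0.194, about 19 points, which is wider than the 15-point target.

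**The case against.** The plan states no response rate, so strictly its figures are unsupported rather than provably false. They can be attained at the extreme: exact enumeration for 84% vs 99% gives 84.8%. The Background does contain an 84%, but it is the share at or above goal (46% + 38%). Levels above 1.1 IU/ml are not successes in this trial, so 84% cannot be the endpoint rate; even if it were, the other group would have to reach 99%.

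The 45% is borrowed. It comes from patients with BMI above 30, whereas this trial enrols from 40. The 46% belongs to the lower dose and rests on 26 patients. The therapeutic ranges used in those studies are not given. All of this stands, and it is why 45% must be labelled an assumption. It does not change the result: placing 0.8 mg/kg at 46% and 1 mg/kg at 31% gives 33.6% (exact 34.3%).

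Direction also matters. The 32–39% range applies to an increase, which is the direction of the primary objective. A fall from 20% to 5% would have 62% power, still well short of 80%.

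Finally, restating the paragraph around 27 points fits the effect to a fixed sample size. That is fair. The restated figure describes what the trial can detect and does not claim that 27 points is plausible.

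**Conclusion.** The concern holds. At the on-target rates the protocol cites, 50 per group gives about 32–35% power for a 15-point absolute difference, not 80%, so a true benefit of that size would be missed about two times in three. About 173 per group would be needed, or else a difference of about 27 points. The stated figures fit only when one group is at essentially 0% or 100%.

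The exact power figure rests on a 45–46% baseline taken from the Background and on reading 15% as absolute. The conclusion does not depend on the baseline within any range the documents support, and the relative reading makes power lower. No attrition allowance is stated, and Section 4 excludes patients whose renal function declines enough to prompt a dose change, so the number analysed, and with it the power, may be lower still. This must be corrected.

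**What to change.** Replace the sample size paragraph in Section 2.h.i with wording such as:

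> Assuming that 45% of the 1 mg/kg group have a therapeutic initial level, 50 patients per group give 80% power (two-sided 0.05) to detect an absolute difference of about 27 percentage points (45% vs 72%). Power for a 15-point difference is about 32–35%.

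If the sponsor had another baseline in mind, state it with its source and recompute the power from it. In Section 2.h.ii, add that the primary result will be reported as a difference in proportions with its 95% CI, and that a non-significant result does not show that the doses are equivalent.

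The cost is wording only: the stated figure becomes less favourable, and no extra patients are needed. Keeping both the 15-point target and 80% power would instead mean about 173 per group, 346 in total rather than 100.

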#### iv. Data Collection

##### 1. Baseline Data

- a. TBW, height, BMI
- b.  $BMI = TBW(\text{kg})/\text{height} (\text{m})^2$
- c. Age, Sex, Race
- d. Scr, CrCl (Cockcroft-Gault equation)
- e. Indication for treatment

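### Randomisation is stratified by BMI, but the strata are undefined and neither planned test uses them; some power is lost if BMI is strongly prognostic and arms are balanced within strata

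*Combined protocol and SAP*

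**What the plan says.** Section 2.d.ii (Procedures) sets the allocation: "Patients will be randomized in a 1:1 fashion into the 0.8mg/kg or 1 mg/kg group (using total body weight) stratified by BMI". It gives no cut-points, no number of strata and no method of balancing within strata. Every eligible patient has a BMI of at least 40 kg/m² (section 2.a.i), so the strata must be subdivisions above 40, and none is named.

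Section 2.d.iv lists "TBW, height, BMI" among the baseline data, so the variable will be available.

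Section 2.h.ii (Statistical Analysis) gives the tests: "Primary outcome will be analyzed using chi-square", and for the secondary outcome "Time to event will be analyzed using survival curves and log rank test". Neither sentence mentions strata or BMI. The sample-size statement in section 2.h.i plans to "detect a 15% difference in the primary endpoint with a 2-sided significance level of 0.05", with 50 patients per arm for 80% power. It does not mention strata either.

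**The concern.** There are two linked gaps. First, because the strata are not written down, the allocation cannot be reproduced or audited, and strata used in any later analysis could be chosen after the data are seen.

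Second, the analysis does not follow the design. Balanced allocation within strata removes the between-stratum component from the true variance of the treatment difference. An unstratified test still charges for that component. If BMI matters for the outcome, the test rejects less often than its nominal level and the precision bought by stratifying never reaches the p-value or the confidence interval. In a trial of 100 patients, a loss that can be avoided at almost no cost should not be built in.

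**Working it through.** **Inputs from the documents.** 50 per arm, two-sided alpha 0.05 and a 15-point difference (section 2.h.i); a reference in-range rate of 45% (Background, study of hospitalised patients with BMI above 30 on 1 mg/kg: "Forty five percent of patients achieved a therapeutic anti-Xa level"). The Background also gives 46% for 26 patients with BMI of at least 40 on a median of 0.8 mg/kg.

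**Assumed, because the documents give nothing.** Two equal BMI strata, 25 patients per arm in each, and a gap *g* between the strata in the in-range rate, varied from 0 to 50 points.

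**Step 1. The plan's own figure.** With d = 0.15 and p̄ = 0.525,

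n = [1.96·√(2·0.525·0.475) + 0.842·√(0.45·0.55 + 0.60·0.40)]² / 0.15² = (1.384 + 0.588)² / 0.0225 ≈ 173 per arm.

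Fifty per arm is not reproduced at these rates. The same formula gives 48 per arm only at 0% vs 15% or 85% vs 100%. At 45% vs 60%, 50 per arm has about 32% power by this approximation. The simulations below give 34%, because the uncorrected chi-square has a true size slightly above 5% at this sample size. This shortfall is a separate issue, but it explains the low power figures here.

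**Step 2. Why the unstratified test is conservative.** Under the null, with overall rate p and strata balanced between arms:

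- variance used by chi-square: (2/n)·p(1−p)
- true variance: (2/n)·[p(1−p) − g²/4]

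For p = 0.45 and g = 0.40, p(1−p) = 0.2475 and the bracket is 0.2475 − 0.04 = 0.2075. The large-sample size is 2[1 − Φ(1.96·√(0.2475/0.2075))] = 2[1 − Φ(2.141)] ≈ 3.2%. For g = 0.20 the bracket is 0.2375 and the size is about 4.5%.

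**Step 3. Simulation of the primary test.** 400,000 trials per row; Pearson chi-square and CMH without continuity correction; a common odds ratio set so that the overall rate rises from 45% to 60%.

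| Gap between strata | Type I error, chi-square / CMH | Power, chi-square / CMH |
|---|---|---|
| 0 points | 5.6% / 5.6% | 34.4% / 34.4% |
| 10 | 5.4% / 5.4% | 34.4% / 34.4% |
| 20 | 5.0% / 5.1% | 34.1% / 34.3% |
| 30 | 4.5% / 4.9% | 33.6% / 34.8% |
| 40 | 3.7% / 5.0% | 33.0% / 37.4% |
| 50 | 2.7% / 5.0% | 32.1% / 41.2% |

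A constant 15-point effect in each stratum gives 33.0% / 37.7% at a gap of 40. At 27 points, about the difference that 50 per arm can detect with 80% power (32.5% vs 59.5%), power is 80.3% / 80.5% at a gap of 20 and 82.1% / 85.8% at a gap of 40.

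**Step 4. The balance condition.** With 50 per arm but strata left unbalanced between arms, chi-square type I error stays at 5.5–5.6% at every gap, so there is no conservatism.

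**Step 5. Log-rank test.** Assumed exponential times, no censoring, treatment hazard ratio 1.5; 40,000 trials per row.

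| Hazard ratio between strata | Type I error, unstratified / stratified | Power, unstratified / stratified |
|---|---|---|
| 1 | 5.5% / 5.4% | 51.6% / 50.0% |
| 1.5 | 4.9% / 5.3% | 48.3% / 49.7% |
| 2 | 4.1% / 5.2% | 44.3% / 49.9% |
| 3 | 3.3% / 5.4% | 37.0% / 50.1% |

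A separate run at a treatment hazard ratio of 1.75 shows the same pattern: 72% / 77% power at a between-strata ratio of 2, and 65% / 78% at 3.

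**The case against.** The strongest reply is that the harm is hypothetical. Up to a 20-point gap the primary test loses at most 0.2 points of power, and no passage supports gaps of 30 to 40 points. Dosing by total body weight already scales dose to size. In the volunteer study in the Background, maximum levels were 1.563 and 1.488 IU/ml in obese and non-obese participants, about 5% apart, although at BMI 30–40. The nearest contrast in morbid obesity is by weight rather than BMI, and was not significant: "The weight cut-off of 150 kg did not result in statistically significant differences in mean anti-Xa levels" (1.12 vs 0.81 IU/ml).

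The outcome is also a two-sided window, 0.5–1.1 IU/ml, so a BMI effect on levels would probably make the dose effect differ by stratum, which a common odds ratio ignores. A check that allows for this assumed lognormal levels, a coefficient of variation of 30–40% and levels at the lower dose scaled by 0.8. CMH gained 0.1 to 0.4 points of power when levels differed by 10% between strata, and 0.5 to 3.9 points at the ratio 1.12/0.81 ≈ 1.38.

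Finally, levels are drawn only after set doses, so time to a therapeutic level will be coarse and heavily tied. The exponential log-rank figures are therefore only indicative.

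All of this stands as a limit on size. It does not supply the missing strata, and it does not give a reason to leave the analysis out of step with the allocation: in these checks CMH with two strata never had lower power than chi-square.

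**Conclusion.** The concern holds. The BMI strata are undefined, and neither planned test uses them. This is not a validity error: type I error is not inflated by ignoring the strata, and the randomised comparison is intact.

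Under the assumed two equal, balanced strata, the loss of power on the primary test is negligible at gaps of 20 points or less, 1.2 points at 30 and 4.4 points at 40. For the log-rank test it is 1.4, 5.6 and 13.1 points at between-strata hazard ratios of 1.5, 2 and 3. If BMI is weakly prognostic, or arms are not balanced within strata, there is little or nothing to recover. The documents do not show which case applies at BMI 40 or more. The change is worth making because it costs so little, but it leaves the sample-size shortfall untouched.

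**What to change.** In section 2.d.ii, state the BMI cut-points, keep the strata few, say how arms are balanced within them, and record each patient's assigned stratum. In section 2.h.ii:

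- Analyse the primary outcome with a CMH test over the randomisation strata, and report a stratum-adjusted risk difference with its 95% CI.
- Stratify the log-rank test for time to therapeutic level by the same strata.
- Keep the simple chi-square as a sensitivity analysis.

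This needs about two sentences and no extra patients or measurements. If BMI turns out to be unrelated to the outcome, simulations at 46% vs 61% put the cost of CMH at 0–0.2 points of power with 2 to 5 strata, 1.2 with 10 and 1.7 with 25. The stratified log-rank test then costs about 1.6 points with two strata (51.6% − 50.0%). These costs are the reason to keep the strata few.
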